# SYNOPSIS

**Primary Objective**

To determine whether oral therapy with TXA results in improvement in serum hemoglobin concentration and/or requirement for PRBC transfusion compared to placebo in patients treated with standard endoscopic ablation, ocreotide and iron supplementation

**Secondary Objectives (if applicable)**

To determine the need for hospitalization for symptomatic anemia or acute gastrointestinal bleed

To determine the need for additional endoscopic interventions

To determine the rate of clinically significant side effects associated with TXA therapy leading to drug withdrawal

**Study Duration**

The interventional portion of the study will be conducted over a 3 month period

**Study Design**

In the RCT portion of the study, we will enroll approximately 50 patients with diagnosed intestinal AEs through VCE and/or endoscopy who experience symptomatic anemia despite standard therapy including endoscopic ablation, octreotide and iron supplementation.

Subjects will be randomized to either the TXA treatment group versus the placebo treatment group for 3 months. Patients will have initial complete blood counts (CBC) measured as a baseline then subsequent CBCs measured at 1, 2 and 3 months. Patients will be monitored for drug side effects, symptoms related to anemia, the need for blood transfusions and hospitalizations related to GI bleeding/anemia.

**Study Population**

All newly diagnosed adult patients with intestinal angioectasias following at the LSU Health Network GI Clinic who meet screening criteria will be considered for inclusion. Existing patients with intestinal angioectasias that are currently not using TXA may also be approached for study participation.

**Number of Participants**

The study design includes 50 participants enrolled in the study

**Number of Study Sites**

The study site includes the LSU Health Network GI Clinic at Ochsner Kenner Hospital

**Primary Outcome Variables**

Primary outcome variables include hemoglobin concentration and the requirement of packed RBC transfusion.

**Secondary and Exploratory Outcome Variables (if applicable)**

Secondary outcome variables include number of hospitalizations, endoscopic interventions and experienced side effects

# 1 - Introduction

## 1.1 Introductory Statement

Intestinal angioectasias are the most common source of small bowel bleeding in the U.S. Over 50% of patients with bleeding angioectasias develop multiple lesions which recur over time. Current medical therapy for angioectasias is suboptimal as many patients continue to experience significant GI blood loss despite currently available standard therapies such as endoscopic ablation and somatostatin analogue therapy (Octreotide). Our goal is to evaluate the efficacy of tranexamic acid as medical therapy for bleeding intestinal angioectasias in a subpopulation of patients who have failed standard therapy or in whom standard therapy is contraindicated.

## 2 - Background

### 2.1 Background/prevalence of research topic

Suspected small bowel bleeding (SSBB) is defined as iron deficiency anemia attributed to chronic gastrointestinal (GI) blood loss or overt GI bleeding which remains undefined in etiology after standard upper and lower endoscopy. SSBB accounts for 5% of all GI bleeding cases. Although missed lesions in the upper GI tract and colon should be considered, up to 75% of patients with SSBB are confirmed to have bleeding sources in the small bowel. Small bowel angioectasias (AE), which are also referred to as angiodyplasias or arterio-venous malformations, are identified as the source of bleeding in 30-40% of all SSBB cases and are the most common small bowel bleeding source in patients older than 50. While AEs can be found throughout the entire GI tract, they are most commonly found in the small bowel specifically in the jejunum, followed by duodenum, stomach and right colon. The prevalence of gastrointestinal AE is estimated to be 0.9-3.0% in non-bleeding patients and up to 6% in patients with evidence of blood loss.

AE's are a collection of dilated submucosal vessels composed of thin tortuous capillaries accompanied by ectasia of the overlying mucosal venules and capillaries. Per Yano-Yamamoto's accepted endoscopic classification system, small bowel AE are classified as type 1 lesions. These lesions are further subclassified as type 1a which are characterized by punctate erythema (<1mm) with or without oozing and type 1b which are classified as patchy erythema (2-3 mm) with or without oozing. Histopathologically, AE consist of thin, dilated and tortuous veins that lack a smooth muscle layer, which is thought to explain their weakness and tendency to bleed.

#### Pathophysiology and Risk Factors

While the pathogenesis and etiology of gastrointestinal AE remains unclear, two developmental theories exist. The first by Regula et al. suggests that chronic intermittent obstruction of veins as they pass through the muscular layers of the bowel wall may cause dilation and increased pressure within the vessels. Due to chronic hypoperfusion, sympathetic nerve stimulation leads to relaxation of intestinal vascular smooth muscle, causing local vascular overload, dilation, and eventually, permanent AE. Dysregulated angiogenesis termed the "angiogenic theory" is an alternative theory which was first suggested by Junquera et al. They found that the expression of basic fibroblast growth factor and vascular endothelial growth factor (VEGF), both central mediators in angiogenesis, were significantly increased in patients with gastrointestinal AEs.

Angioectasias are rarely seen in patients younger than age 50 except in cases of hereditary hemorrhagic telangiectasia (HHT). Patient age is the primary risk factor for AE but these lesions have been associated with additional risk factors. Chronic renal failure, particularly end-stage renal disease, has been shown to predispose patients to the development of AEs due to uremic and metabolically driven platelet dysfunction. Aortic stenosis (AS) has also been studied extensively in association with development of AEs, an association known as Heyde syndrome, which may be related to an acquired form of von Willebrand disease. Bleeding due to AEs has also been associated with left ventricular assist device (LVAD) placement. Additional risk factors include tobacco use, obesity, use of antithrombotic agents, use of non-steroidal anti-inflammatory drugs and chronic liver disease.

### *Diagnosis of AEs*

With the introduction of video capsule endoscopy (VCE) and device-assisted enteroscopy (DAE) in 2001, previous studies for SSBB including small bowel follow through, angiography, cross sectional imaging and nuclear scans are less commonly employed. Due to the anatomic features of the small bowel, conventional endoscopy provides limited evaluation of the deep small bowel. VCE is a simple noninvasive procedure which is well tolerated by patients. Per the American Gastrointestinal Associate (AGA) guidelines, VCE is the first line investigation for small bowel evaluation in hemodynamically stable patients with no evidence of obstruction. DAE is usually reserved to pursue positive VCE findings that require intervention or in the setting of high clinical suspicion for small bowel lesions despite negative VCE study. A large meta-analysis study by Pasha et al. found the diagnostic accuracy of VCE (60%) was similar to that of BE (57%).

### *Interventional Management*

Endoscopic management of AEs is difficult and only made possible through the relatively recent advent and development of BE. Endoscopic ablation using argon plasma coagulation (APC) is the most common technique used to treat gastrointestinal AE. Other endoscopic techniques include bipolar electrocautery, sclerotherapy injection and mechanical hemostasis using hemo clips or banding, which may be beneficial in larger lesions. A number of studies report an improvement in Hb, a reduction in transfusions and an improvement in overt bleeding following APC therapy for AE's. However, retrospective studies suggest a high re-bleeding rate of up to 60% for small bowel AEs with or without thermal intervention using double balloon enteroscopy, especially in those patients who required large amount of transfusion before DAE and those with multiple vascular lesions.

Radiological embolization is a treatment technique considered for patients with active GI bleeding who are hemodynamically unstable or on which endoscopic therapy has failed. Mesenteric angiography is used to identify bleeding vessels which are subsequently embolized with micro-coils. Although the rate of hemostasis achieved by embolization is high, early recurrent bleeding was found to occur in an estimated 20% of patients. Moreover, severe complications such as arterial dissection and bowel infarction occurring in up to 17% of patients is a major limitation of embolization techniques.

If the above therapies have been exhausted and medical management has been unsuccessful, surgical management is sometimes required. Small bowel surgical resection is reserved for situations when all other forms of management have failed or in an emergent setting due to massive blood loss. Surgery is not commonly seen for the management of small bowel AEs secondary to the high mortality and morbidity as many patients are elderly with significant comorbidities.

### *Medical therapies*

Medical therapy is an important adjunct to endoscopic ablation in patients with AE's as the majority of patients have multiple lesion which may be difficult to completely ablate with new lesions developing over time. Pharmacological treatments including iron supplementation, somatostatin analogues, hormonal therapies and thalidomide have been considered for patients who have not responded well to endoscopic intervention with APC or in whom endoscopy is contraindicated. Conservative management with iron supplementation given orally or intravenously is a mainstay of treatment for mild intestinal AE bleeding. This not only helps maintain an adequate level of hemoglobin but helps reduce the frequency of transfusion. In

more severe bleeding, transfusion of packed RBCs is an essential element of treatment, particularly when mechanistic and medical methods fail.

Somatostatin analogues including octreotide and lanreotide have been used to treat AE. Hypothesized mechanisms include decreased duodenal and splanchnic blood flow, improved platelet aggregation, increased vascular resistance and inhibition of angiogenesis. Through a meta-analysis, Brown et al. report a clinical response rate of 76% compared to the natural progression of the disease and reduced blood product requirements. More recently, Nardone et al. performed a retrospective analysis and found that 40% of patients had a reduction of transfusion requirements over a 6-year mean follow up period. There have been no randomized control trials performed to prove the efficacy and safety of somatostatin analogues compared to other treatment options.

Hormonal therapies, predominantly estrogen and progesterone, were initially thought to be useful in the management of intestinal AE in historical studies during the pre-VCE era. However, due to the inability to visualize the small bowel the precise nature of what was treated was unknown. The proposed mechanism of action includes stabilization of the vessels through keratinization, increase in the number of circulating activated platelets, inhibition of angiogenesis and decreased mesenteric blood flow. While early small scale studies were promising, Junquera et al. reported the only controlled randomized control trial which found there was no reduction in transfusion or iron therapy needs in the patients on hormone therapy vs placebo therapy. The frequency of side effects and limitations for use in patients at risk for thromboembolic events, have resulted in hormonal therapy having only a limited role in the treatment of small bowel bleeding.

Therapies utilized to inhibit angiogenesis in cancer patients have been studied due to their potential for inhibition of angiogenesis in the development of new AE's. Thalidomide, an immunomodulatory drug with antiangiogenic properties, has been used to treat small bowel AEs when conventional therapies have been unsuccessful. These studies have shown a significant reduction in bleeding episodes and an increase in mean hemoglobin concentration after treatment with thalidomide. However, the use of thalidomide is limited by severe side effects including thromboembolism, hematological abnormalities and teratogenicity.

As previously discussed, gastrointestinal AE's are known to strongly express vascular endothelial growth factor (VEGF). Bevacizumab is a known anti-VEGF monoclonal antibody that has shown to be effective in decreasing bleeding events and the need for blood transfusions in patients with HHT. Although effective, bevacizumab therapy is complicated by serious adverse events which include arterial thrombosis, thromboembolic events, heart failure and nephrotic syndrome in up to 10% of patients. Further, another barrier to utilization is securing financial coverage through insurance as most plans do not cover the mono-clonal antibody. Aminocaproic acid is a closely related fibrinolytic inhibitor, similar to our trial drug tranexamic acid. It is a lysine analog that inhibits plasminogen activators to promote hemostasis. Few case reports have shown therapeutic success in treating upper GI bleeds secondary to radiation gastritis and gastric cancer. Further research is needed to understand appropriate dosing regimens and the side effect profile.

### Tranexamic Acid

Tranexamic acid (TXA) is a hemostatic agent that is a synthetic reversible competitive inhibitor to the lysine receptor found on plasminogen. TXA works by forming a reversible complex that displaces plasminogen from fibrin resulting in the halting of fibrinolysis. TXA has been approved by the FDA for the treatment of heavy cyclic menstrual bleeding and tooth extraction in patients with hemophilia. The antifibrinolytic agent has been further studied in the management of major bleeding in multiple clinical settings including trauma, obstetrics and neurosurgery. TXA has been considered a potential adjunctive treatment for GIB with the earliest RCT conducted in 1973. With the recent publication of the large HALT-IT trial, which explored the use of high dose TXA over 24 hours in the setting of acute GI bleed, there has been an increasing interest in the possible applications of TXA.

The literature contains a few case reports commenting on the successful use of TXA in patients with AE's, without increasing the risk of thromboembolic events. Of note, there does exist a randomized placebo-controlled trial examining the use of oral TXA for acute lower GI bleeds requiring hospitalization. Smith et al. found no improvement in average hemoglobin and transfusion rates following a four-day treatment regimen with oral TXA, however, the bleeding source for approximately 50% of the study population was diverticular in nature. Moreover, there are no current case series or randomized control trials examining the use of TXA in patients with persistent or progressive anemia due to chronic GI blood loss from AEs despite standard treatment with endoscopic ablation and iron supplementation.

The common side effects of TXA include nausea, vomiting, diarrhea, rash, itching, hypotension, and thromboembolic events as reported by the FDA. Contraindications include a history of venous or arterial thromboembolism, intracranial bleeding or active thromboembolic disease. TXA is not well studied in the renally impaired patient however it is 95% excreted in urine so renal dosing is recommended. Dionne et al. recently published the largest systemic review and meta-analysis examining TXA in GIB and found that the absolute risk of thromboembolic events to be <1%. This presents a small but statistically significant risk of DVT/PTE with high dose IV TXA but cannot be extrapolated to lower dose oral TXA regimens. Further, the safety profile of TXA has been confirmed and well-studied in the fields of trauma and orthopedics.

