## **2.2 Prior clinical experience**

The principal investigator for this study has been using TXA in his clinic as an off-label drug for the treatment of small bowel AEs. Those who were treated with TXA were those patients that have failed standard therapy. Failure of standard therapy is defined as continued GI bleeding and need for blood transfusions despite endoscopic ablation, octreotide therapy and iron supplementation for at least 3-6 months. Thus far, 9 patients have been treated with TXA therapy consisting of 650 mg oral tablets taken three times per day for 3 months. In 8 of those patients there was an observed clinical response defined as stabilization of hemoglobin which was not previously achieved with prior therapy. Although this sample size of patients was not a controlled study accounting for confounding variables, it does strongly highlight the potential beneficial therapeutic effects of TXA. Of note, there were no side effects observed by the 9 patients.

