### 3.3 Potential Risks and Benefits

#### 3.3.1 Potential Risks

Adverse events will include medication side effects including nausea, vomiting, diarrhea, rash, itching, hypotension, and thromboembolic events. These side effects will be closely monitored through monthly in person or virtual interviews with patients for the entirety of the study period.

Thromboembolic events have the largest potential impact to patient's health and include deep vein thrombosis (DVT), pulmonary embolism (PE) and stroke. Dionne et al. recently published the largest systemic review and meta-analysis examining TXA in GIB and found that the absolute risk of thromboembolic events to be <2%. This presents a small but statistically significant risk of DVT/PTE with high dose IV TXA but cannot be extrapolated to lower dose oral TXA regimens. Further, the safety profile of oral TXA has been confirmed and well-studied in the fields of trauma and orthopedics. Specifically, a large meta-analysis looking at the 5 RCTs comprising approximately 600 patients found no statistically significance increasing in thromboembolic complications between patients undergoing a total knee replacement who received oral TXA for intra/post-operative bleeding vs control patients. We do appreciate that certain populations of patients are at increased risk for thromboembolic events. These include comorbidities such as liver disease and malignancy. On literature review, specific rates of thromboembolic events in these populations with the use of TXA has not yet been studied. Importantly, a group of patients who may not know they would be at an increased risk are those with undiagnosed prothrombotic states. While it would not be possible to screen for all prothrombotic diseases, factor 5 Leiden and prothrombin mutation make up a large portion of hypercoagulable disorders. In order to screen out these patients, lab markers testing for the aforementioned disorders will be ordered in all patients during initial laboratory lab work.

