**Exclusion Criteria**

- Contraindications to TXA therapy
  - Allergy to TXA, intracranial bleed, history of venous or arterial thromboembolism, active thromboembolic disease, ischemic retinopathy
- Bleeding/Coagulopathy disorder and/or on anticoagulation regimen
- Ulcerative colitis or Crohn's disease
- End stage renal disease
- Decompensated cirrhosis
- Pregnancy or intention to become pregnant
- Patient refusal of blood products because the secondary outcome is pre-determined
- Unable to give formal consent
- Participation in another interventional study where primary outcome includes hemoglobin/hematocrit values
- Inability to adhere to treatment regimen for 3 months
- Non-English speaking
- Patients < 18 years old

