#### 6.1.1 Dosage, Admin, Schedule (if applicable)

Patients in the intervention group will be treated with TXA 650 mg three times per day for 3 months. This dosing regimen has been studied in patients with heavy menstrual bleeding and found to be beneficial with limited side effects.

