**6.2.3 Pharmacokinetics (if applicable)**

The bioavailability of oral TXA is 30-50% of the ingested dose and is not affected by food intake. Urinary excretion is the primary means of TXA elimination with 95% of an administered dose being processed by the renal system. The half-life of IV TXA was found to be 2 hours with the mean terminal half-life as approximately 11 hours

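### The protocol says renal dosing of TXA is recommended, yet fixes one dose for the whole TXA arm, excludes only end stage renal disease and requires no renal function test

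*Combined protocol and SAP*

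**What the plan says.** Two places describe how the drug is cleared. Section 2.1 (Tranexamic Acid) states that "TXA is not well studied in the renally impaired patient" and, in the same sentence, that "it is 95% excreted in urine so renal dosing is recommended". Section 6.2.3 repeats the pharmacology in the methods: "Urinary excretion is the primary means of TXA elimination with 95% of an administered dose being processed by the renal system".

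The operative sections do not carry this through. Section 6.1.1 reads: "Patients in the intervention group will be treated with TXA 650 mg three times per day for 3 months". It has no lower dose tier. The exclusion list in 5.3.2 has one renal item, "End stage renal disease", and its sub-list of TXA contraindications has none.

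The laboratory tests named are a CBC at baseline and at months 1, 2 and 3 (Synopsis and 5.1), markers for two inherited thrombophilias (3.3.1) and a serum pregnancy test (6.2.1). Section 6.3.3 defines the baseline laboratory work only by pointing back to what was already stated. Section 6.3.4 adds only that it comes before treatment starts. The withdrawal rules in 6.3.6 contain no renal trigger.

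**The concern.** A dosing recommendation that the authors accept should appear in the dose section, in the eligibility criteria, or in a test that finds the patients it applies to. Here it appears in none of them, apart from the exclusion of the most severe stage.

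The gap is relevant to this population. Section 2.1 (Pathophysiology and Risk Factors) says: "Chronic renal failure, particularly end-stage renal disease, has been shown to predispose patients to the development of AEs". Candidates with impairment short of end stage are therefore plausible, and nothing in the plan requires anyone to look for them.

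What is at stake is the safety of some TXA-arm patients over 3 months of treatment. Placebo patients are not exposed to the drug. The protocol already uses a laboratory screen to limit one drug risk, the thrombophilia markers in 3.3.1. It has no comparable check on the route that clears most of the drug.

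**Working it through.** The plan states no figure on this point, so there is nothing to reproduce. The main check compares the recommendation with each section that could implement it.

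**1. Where the recommendation could take effect**
- Dose (6.1.1): one dose for all TXA patients, 650 × 3 = 1950 mg/day, with no adjustment.
- Eligibility (5.3.2): only end stage renal disease is excluded.
- Detection (Synopsis, 3.3.1, 5.1, 6.2.1, 6.3.3, 6.3.4): CBC, two thrombophilia markers and a pregnancy test. No creatinine, eGFR or metabolic panel is named at screening, at baseline or on treatment.
- Stopping or changing dose (6.3.6): no renal rule.

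A patient with impairment short of end stage passes every step and, if allocated to TXA, receives the full dose. The consent pages were not available and might mention further tests, but the procedure sections are present and name none for renal function.

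**2. How many patients (assumed range)**
The documents give no prevalence. Let p be the share of eligible patients with impairment to which the recommendation applies. With 25 TXA patients (6.1.2), the expected number is 25p and the chance of at least one is 1 − (1 − p)^25.
- p = 1%: 0.25 patients; 22%
- p = 5%: 1.25 patients; 72%
- p = 10%: 2.5 patients; 93%
- p = 20%: 5 patients; 99.6%

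These values only restate the assumption. They show that the answer depends on a prevalence the plan does not supply.

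**3. Exposure (illustration only)**
Take the 95% as the renal share of clearance, and let r be kidney function relative to normal (assumed). With linear kinetics, renal clearance proportional to r, and unchanged absorption and non-renal clearance, the exposure ratio on the same dose is 1 / (0.05 + 0.95r).
- r = 0.50: 1 / 0.525 = 1.90
- r = 0.30: 1 / 0.335 = 2.99

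The 30–50% oral bioavailability in 6.2.3 cancels in the ratio. The calculation shows why a renal dosing recommendation makes sense for this drug. It does not show that either level is unsafe.

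**4. Recruitment cost of an exclusion**
If a share p (assumed) falls below the cut-off, 50 / (1 − p) otherwise eligible patients are needed to randomise 50. For p = 5%, 10% and 20% this is 52.6, 55.6 and 62.5, rounded up to 53, 56 and 63. Section 7.6 lists insufficient recruitment, at 80% of plan, as a reason to discontinue: 0.80 × 50 = 40. If only 50 otherwise eligible patients could be found, a 20% exclusion would leave exactly 40.

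**The case against.** The strongest reply is that no harm is demonstrated. The recommendation is a single clause resting on a cited source, with no threshold, adjusted dose or named consequence. The documents do not show that 1950 mg/day is too much at any level of function short of end stage. The group that the background singles out, end stage disease, is already excluded. All of this stands, and it limits the point to a mismatch within the protocol.

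The safety context is also fairly mild. The protocol puts the thromboembolic risk below 1% in section 2.1 and below 2% in 3.3.1, ties it to high-dose intravenous use, and says it "cannot be extrapolated to lower dose oral TXA regimens". Section 2.2 says that "there were no side effects observed by the 9 patients" who took this regimen. Section 2.1 also cites case reports of successful use, one of them in dialysis patients by its title. These weaken any claim of high risk but do not settle the question: the renal function of the nine is not stated, and the dose in the dialysis report is not given. Equally, no section links renal impairment to thromboembolism, so the contrast with thrombophilia screening concerns consistency and is not evidence of risk.

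Monitoring is planned. Section 6.2.2 provides biweekly calls, monthly visits, prompt follow-up of new symptoms and a dedicated phone line. This deserves credit, although it picks up symptoms and does not measure renal function.

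A reader might infer that impaired patients would go unrecognised. The documents do not support that. Candidates attend this clinic, their records may show renal function, and applying the end stage exclusion needs some review of renal status. What is established is that the protocol does not require them to be identified.

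**Conclusion.** The inconsistency is real and should be fixed. The protocol recommends renal dosing, then sets a uniform dose, one renal exclusion at the extreme, and no test that would show who else is affected. Following the plan exactly could therefore dose some TXA patients against its own advice. This is more than missing detail, because 6.1.1 gives a definite instruction that does not allow for the recommendation.

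The number of patients, the relevant threshold and the added risk are all absent from the documents. The prevalence and exposure figures above rest on stated assumptions. Confidence is medium for that reason.

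Two stronger conclusions might be drawn, and neither is supported. One is that renally impaired patients would be harmed or overdosed: no unsafe exposure level is given, so the added risk is unknown and not shown to be high. The other is that the hemoglobin comparison would be biased: allocation is random with respect to renal function, and nothing in the plan suggests a distortion between arms.

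**What to change.** Add serum creatinine with eGFR to the baseline draw already planned in 6.3.3 and 6.3.4, and require the result before randomisation. Then choose one of two rules before enrolment begins:

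- **Preferred:** add an eGFR exclusion to 5.3.2, with the cut-off fixed by the clinical team. The documents give no threshold, so none is proposed here. Because exclusion precedes allocation, no randomised patient is removed and 6.1.2 can still fill 25 per arm.
- **Alternative:** pre-specify in 6.1.1 a reduced dose below the cut-off, matched in both arms so that the blind is kept.

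Either way the cost is a protocol amendment and one more analyte on an existing draw. The exclusion also narrows the population and shrinks the pool at a single site (5.1.2) with a three-month recruitment window (5.1.1), and should be weighed against the recruitment cut-off in 7.6. The reduced dose keeps those patients, but changes the regimen under test for them and needs matching blinded supply under 6.1.3. A single baseline value will not track renal function during treatment.
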